##### Modified Cigarette Evaluation Questionnaires

Responses on the 7-point scales for each mCEQ (mCEQ-V for days in which VERVE® products are used and mCEQ-C for days in which subject's OB cigarettes are used) will be treated as continuous variables and the following factor scores will be calculated according to the literature:

- Smoking satisfaction: average of the response scores from questions 1, 2, and 12;
- Psychological reward: average of the response scores from questions 4 to 8;
- Aversion: average of the response scores from questions 9 and 10;
- Enjoyment of sensation: response score from question 3;
- Craving Reduction: response score from question 11.

The following variable will be determined for each factor score.

- Actual score

##### Use Product Again Questionnaires

The analysis variable will be the response VAS score to the Use the Product Again questionnaire for each product. In addition, responses to Use the Product Again questionnaire will also be treated as bipolar variable and used as an analysis variable. The bipolar score is calculated by subtracting 50 from the original VAS score, then categorizing into three categories: -50 to <0, 0, and >0 to 50.

## 7.2 Data Summary and Presentation

The descriptive statistics tables for blood and urine biomarkers, products used per day, and subjective effects will be generated with the following level of precision for the summary statistics:

The derived values (amount excreted in urine biomarkers, change and percent change from baseline) will have two decimal points.

- Number of observations (n)/number of missing values (n missing) without a decimal;
- Mean/median with one more decimal/significant figure than minimum/maximum;
- Q1 and Q3 with one more decimal/significant figure than minimum/maximum;
- Standard deviation/standard error of the mean (SD/SEM) with one more decimal/significant figure than mean/median.
- Coefficient of variation (CV%) with one decimal;
- Minimum/maximum in same precision as in the database
- 95% confidence intervals (CI) with one more decimal/significant figure than minimum/maximum

### 7.2.1 Demographic Summary

Descriptive statistics will be summarized for continuous demographics variables (e.g., age, weight, height, and BMI) and frequency counts will be tabulated for categorical demographics variables (e.g., gender, ethnicity, race, income level, and highest education grade level) by study group, and overall. The variable BMI is calculated from the weight and height collected at the Screening assessment and age is calculated from the date of the Screening visit. Subjects only enrolled in the product trial period (dropped prior to randomization) will be summarized separately as a group.

The Safety, mITT and PP populations will be used for this summary.

### 7.2.2 Smoking History

CPD including Days -2 through -1 collected on site, years of smoking (calculated from Screening date), Fagerström Test for Cigarette Dependence scores (individual questions and total score), and usual brand, brand style, flavor, and cigarette size reported at Screening will be listed. Descriptive statistics will be summarized by study group and overall for continuous variables and frequency counts and percentage will be presented for categorical variables. Subjects only enrolled in the product trial period will be summarized separately as a group.

The Safety, mITT and PP populations will be used for this summary.

### 7.2.3 Urine BOE

Urine biomarker concentration (including each component of NE), urine creatinine concentration, and the creatinine-adjusted urine biomarker concentration will be listed by subject and study day for all urine biomarkers. All BLQ values will be presented as “BLQ” in the listings.

Urine biomarker mass excreted per 24 hours, absolute change from baseline and percent change from baseline of total mass excreted per 24 hours, and creatinine-adjusted urine biomarker concentrations, will be summarized by group and study day for all urine biomarkers using descriptive statistics (n, n missing, mean, SD, CV%, SEM, minimum, median, maximum, and 95% CI). The descriptive statistics will be provided for both mITT and PP populations.

### 7.2.4 Blood BOE

Blood biomarker concentrations will be listed by subject and study visit for COHb. All BLQ values for COHb will be presented as “BLQ” in the listings.

Blood biomarker concentration, absolute change from baseline blood biomarker concentration, and percent change from baseline biomarker concentration will be summarized by group and study day using descriptive statistics (n, n missing, mean, SD, CV%, SEM, minimum, median, maximum, and 95% CI). BLOQ COHb saturation will be treated as one-half the LLOQ. The descriptive statistics will be provided for both mITT and PP populations.

### 7.2.5 Product Use

#### Product Use

Number of CPD smoked per day (Groups 1, 2, and 3, only), number of VPD per day (Groups 2, 3, 4, and 5 only), average duration of VERVE® product used per use each day (Groups 2, 3, 4, and 5 only), and total duration of VERVE® product use per Day (Groups 2, 3, 4, and 5 only) will be listed by subject and study day and summarized by group and study day using descriptive statistics (n, n missing, mean, SD, CV%, SEM, minimum, Q1, median, Q3, maximum and 95% CI). The start time of VERVE producct use along time of the day (x-axis, 7:00 to 23:00) by group (y-axis, Group 2, 3, 4, 5) for Day 1, 5, 7 (one plot per day) will be plotted.

Product use analyses will be performed on the mITT dataset.

### 7.2.6 Questionnaires

The responses and the factor scores from the QSU-Brief will be listed by subject, study day and collection time. Factor scores (original scores, and change from pre-use scores) will be summarized by group, day and collection time using descriptive statistics (n, n missing, mean, SD, CV%, SEM, minimum, Q1, median, Q3, maximum, and 95% CI).

The mCEQ will be considered as a 7-point scale and treated as a continuous variable. The responses from mCEQ-C or mCEQ-V and factor scores will be listed by subject and study day. The factor scores will be summarized by group and study day using descriptive statistics (n, n missing, mean, SD, CV%, SEM, minimum, Q1, median, Q3, maximum and 95% CI).

Responses to Use the Product Again questionnaire recorded as VAS scores will be treated as bipolar variable and summarized by study group, study product and category using frequency count tables. The original response VAS score and bipolar score for the Use the Product Again questionnaire will be summarized using descriptive statistics (n, n missing, mean, SD, CV%, SEM, minimum, Q1, median, Q3, maximum and 95% CI).

These analyses will be performed on the mITT dataset.

## 7.3 Statistical Analyses

### 7.3.1 Primary Endpoint Analysis

A linear mixed model for repeated measures (MMRM) analysis will be used for comparing each test group (Groups 2-5) to the control group (Group 1 and Group 6) in the primary endpoint (24-hour total urinary NNAL (mg/24 hours) excreted on Day 7). In the model, study group, study day, and study group by study day interaction, and gender are the fixed effect factors. The baseline value of the response biomarker is the covariate. A restricted maximum likelihood estimation method will be applied and several covariance structures will be tried. Five candidate covariance structures will be considered: compound symmetry, 1st order autoregressive, 1st order autoregressive with a random subject effect, unstructured and Toeplitz. The most appropriate covariance structure will be determined based on the AIC criteria (the covariance structure with the smallest AIC will be chosen). The least-square mean, 95% confidence interval and p-value will be provided for the study groups. The least-square mean difference, 95% confidence interval and p-value will be provided for the study group comparisons. Pairwise comparisons (Group 2 vs. Group 1, Group 3 vs. Group 1, Group 4 vs. Group 1, Group 5 vs. Group 1, Group 2 vs. Group 6, Group 3 vs. Group 6, Group 4 vs. Group 6, and Group 5 vs. Group 6,) will be performed using a Dunnett's test at a 2-sided significance level of 0.05 to adjust for multiplicity. Group 1 & 6 will be considered as the control groups. The test is for each of the other groups to compare with the control groups. The analysis will be conducted on the mITT and PP datasets.

The following SAS codes will be used to perform the analysis.

```
Proc mixed data=<>;
Class subject gender group day;
Model response = gender group day group*day baseline/ddfm=kr;
Repeated day/type=<type> subject=subject;
LSmeans group*day/CL alpha=0.05 pdiff dunnett ('1'*Day 7, '6'*Day 7);
```

Run;

Note: This model will include both the Day 7 value (primary endpoint) and interim time points (Day 5, secondary endpoint). The above analysis will also output the residual diagnosis to check for normality and to identify outliers).

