## **11.2 Sample Size Estimation**

This study is designed to evaluate changes in exposure to selected HPHC when adult smokers partially or completely switch to oral tobacco-derived nicotine VERVE® Chews or VERVE® Discs compared to those who continue smoking cigarettes or stop using all tobacco products. Assuming a similar effect size for the new study as for the previous ALCS study (ToPP4ST\_1011\_07) between the continued cigarette smoking group and each of the two dual usage groups ( $\geq 50\%$  CPD reduction with VERVE® DISCS or VERVE® CHEWS), a two-sided t test, 85% power and an  $\alpha = 0.025$  Type I error rate to account for the multiplicity adjustment for the two comparisons, 35 subjects are needed to complete for the continue cigarette smoking group and the dual usage groups. We expect that the effect will be larger in the VERVE® only and smoking cessation groups, so 25 subjects are needed to complete in these groups.

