### **11.9 Statistical Analysis**

Linear mixed models for ANCOVA will be used to compare the Day 5 and Day 7 biomarker values and subjective effects questionnaire scores between groups as described in the study objectives. In the statistical models, the outcome variable will be included as a dependent variable; group, and gender will be included as fixed effects; and baseline values/scores will be included as covariates. The SAS Proc Mixed procedure will be used. The LSM difference and 95% confidence interval for the LSM difference between the Test and Reference Groups will be provided.

Normality and equal variance assumptions will be tested for biomarker variables. An appropriate data transformation will be used if parametric assumptions for the distribution of above-mentioned data are markedly violated.

The statistical significance level will be 5% for two-sided testing. Adjustments for multiple comparisons will not be made.

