### **7.3.1.1 Multiplicity adjustment**

There is one primary analysis variable. No multiplicity adjustment will be done among biomarkers. For the test groups compared to the reference groups for each biomarker, Dunnett's method will be used for the adjustment of multiple comparisons.

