# **9. SUMMARY OF CHANGES FROM PROTOCOL-PLANNED ANALYSIS**

The analyses described in this SAP are aligned with those analyses described in the protocol with the following changes for statistical analysis.

1. Mixed model with repeated measurement instead of mixed model will be used in the analysis for biomarker statistical analysis as there are two response values (Days 5 and 7) for each subject.
2. Emax for Use Product Again questionnaire was mentioned in the protocol. As the Use Product Again questionnaire will only be conducted at Day 7 and only one response value for each subject, no maximum value will be available. The analysis will be performed based on the original response.
3. The statistical analysis model for Use Product Again questionnaire was modified based on the study design and data collection.

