Group 2 vs Group 1	5	X.XX (X)	X.XX (X)	XXX.XX	XX.XX - XXX.XX
	7	X.XX (X)	X.XX (X)	XXX.XX	XX.XX - XXX.XX
Group 3 vs Group 1	5	X.XX (X)	X.XX (X)	XXX.XX	XX.XX - XXX.XX
	7	X.XX (X)	X.XX (X)	XXX.XX	XX.XX - XXX.XX
Group 4 vs Group 1	5	X.XX (X)	X.XX (X)	XXX.XX	XX.XX - XXX.XX
	7	X.XX (X)	X.XX (X)	XXX.XX	XX.XX - XXX.XX
Group 5 vs Group 1	5	X.XX (X)	X.XX (X)	XXX.XX	XX.XX - XXX.XX
	7	X.XX (X)	X.XX (X)	XXX.XX	XX.XX - XXX.XX
Group 2 vs Group 6	5	X.XX (X)	X.XX (X)	XXX.XX	XX.XX - XXX.XX
	7	X.XX (X)	X.XX (X)	XXX.XX	XX.XX - XXX.XX
Group 3 vs Group 6	5	X.XX (X)	X.XX (X)	XXX.XX	XX.XX - XXX.XX
	7	X.XX (X)	X.XX (X)	XXX.XX	XX.XX - XXX.XX
Group 4 vs Group 6	5	X.XX (X)	X.XX (X)	XXX.XX	XX.XX - XXX.XX
	7	X.XX (X)	X.XX (X)	XXX.XX	XX.XX - XXX.XX
Group 5 vs Group 6	5	X.XX (X)	X.XX (X)	XXX.XX	XX.XX - XXX.XX
	7	X.XX (X)	X.XX (X)	XXX.XX	XX.XX - XXX.XX

Note: The mixed model for repeated measures includes study group, study day, study group by study visit interaction, and gender as fixed effects, baseline (Day -1) value as the covariate with a variance-covariance matrix based on the AIC value.

Final variance-covariance matrix is XXX.

Test = The first group in the comparison

Reference = The second group in the comparison

n = Number of observation used in the analysis

Dunnett-Hsu adjusted confidence interval and p-value are reported.

Group X = <description of groups>

Program: /CAXXXX/sas\_prg/pksas PROGRAMNAME.SAS DDMMYYYY HH:MM

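### The 85% power was computed for two comparisons at alpha 0.025, but the SAP tests them inside a wider Dunnett family and Protocol 11.9 says no adjustment, so the figure does not describe the planned primary test

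*SAP*

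**What the plan says.** The documents give three multiplicity rules for the same primary endpoint.

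- **Sample size (Protocol 11.2, repeated in SAP 4).** The basis is "a two-sided t test, 85% power and an" alpha of 0.025, described as the "Type I error rate to account for the multiplicity adjustment for the two comparisons, 35 subjects are needed to complete" in Groups 1–3. The two comparisons are each dual-use group (2 and 3) against continued smoking (1), which is also the primary objective and hypothesis. Groups 4–6 need 25 completers each.
- **Protocol 11.9.** "The statistical significance level will be 5% for two-sided testing. Adjustments for multiple comparisons will not be made".
- **SAP 7.3.1 and 7.3.1.1.** Eight pairwise comparisons are listed, Groups 2–5 against Group 1 and Groups 2–5 against Group 6, and these "will be performed using a Dunnett's test at a 2-sided significance level of 0.05 to adjust for multiplicity". SAP 7.3.1.1 repeats it: "For the test groups compared to the reference groups for each biomarker, Dunnett's method will be used for the adjustment of multiple comparisons".

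The SAP's code line is "LSmeans group*day/CL alpha=0.05 pdiff dunnett ('1'*Day 7, '6'*Day 7". The shell for Table 14.2.1.1.5.2 shows all eight comparisons at Day 5 and again at Day 7, with the footnote "Dunnett-Hsu adjusted confidence interval and p-value are reported".

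SAP 9 opens with "The analyses described in this SAP are aligned with those analyses described in the protocol with the following changes for statistical analysis" and lists three items: the repeated-measures model, the dropped Emax, and the Use the Product Again model. Multiplicity is not among them.

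**The concern.** The threshold that a primary contrast must pass depends on how many comparisons share its family. The sample size assumed two. The SAP puts the two primary contrasts in with comparisons that its own objectives class as secondary (exclusive use against smoking, and everything against cessation), so the primary test is held to a stricter threshold than the one it was sized for.

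The family is also undefined. Four comparisons against each of two controls and eight comparisons jointly give different critical values. The code does not settle this. It is schematic, works on group-by-day means and names only Day 7 control cells, whereas the table reports contrasts within Day 5 and within Day 7. Two programmers could produce different primary p-values and confidence intervals from the same SAP, and a reader who follows Protocol 11.9 would expect a third set.

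**Working it through.** **Inputs from the documents.** 35 completers in each of Groups 1–3 and 25 in each of Groups 4–6; two-sided alpha 0.025; 85% power; two-sample t test (Protocol 11.2, SAP 4). Enrolment is 40 and 30 per group. No effect size or SD is given; the effect is taken from an earlier sponsor study.

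**Step 1: the effect size the plan implies.** The 35 and 85% cannot be reproduced forwards, so solve for d. For n per group, the t statistic is noncentral t with noncentrality d × √(n/2). With n = 35, df = 68 and critical value 2.292 (alpha 0.025), power is 85% when d = 0.798, a noncentrality of 0.798 × √17.5 = 3.34. As a consistency check, the superseded basis shown in the Amendment 1 summary (30 per group at alpha 0.05) implies d of 0.787–0.801, so d of about 0.80 fits both.

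**Step 2: Dunnett critical values.** These were simulated from the joint distribution of the contrasts, with completers 35/35/35/25/25/25 and df = 180 − 8 = 172 (six groups, gender and baseline).

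**Step 3: power per primary comparison at d = 0.798, no covariate gain.** The higher figure uses the pooled 172 df; the lower uses the t test's 68 df at the same per-comparison alpha.

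| Rule for Group 2 (or 3) vs Group 1 | Critical value (172 df) | Per-comparison alpha | Power, 35 completers |
|---|---|---|---|
| Unadjusted 5% (Protocol 11.9) | 1.97 | 0.050 | 91% |
| Planned 0.025 each | 2.26 | 0.025 | 85–86% |
| Dunnett, two primary contrasts | 2.23 | 0.027 | 86–87% |
| Dunnett, four vs Group 1 | 2.47 | 0.014 | 79–81% |
| Eight jointly, two controls | 2.70 | 0.0075 | 72–74% |

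**Step 4: error rates.** With no adjustment, the familywise error for the two primary tests is about 0.091. Two separate four-comparison Dunnett families, one per control, give about 0.092 across the eight, so the two readings of SAP 7.3.1 also differ in overall error.

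**Step 5: what would restore 85%.**

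- *More completers, no covariate gain.* Four comparisons need 39–40 per group. Eight need about 45, more than the 40 enrolled. If all 40 complete (30 in Groups 4–6), power is 85–86% for four and 79–81% for eight.
- *Baseline adjustment.* If the planning d is on the unadjusted scale, adjusting for a baseline with correlation r raises it to d/√(1 − r²); for r = 0.3 that is 0.798/0.954 = 0.837. The documents give no r, so a range is assumed:

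| Assumed r, 35 completers | Four comparisons | Eight jointly |
|---|---|---|
| 0.3 | 83.5–84.6% | 77–79% |
| 0.4 | 87–88% | 81–82.5% |
| 0.5 | 91–91.5% | 86–87% |

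**The case against.** The strongest reply is that no loss of power has been shown. The d of 0.80 is back-solved from an effect the documents do not state, and a planning t test never exactly matches a baseline-adjusted repeated-measures model. The circumstances also favour the trial: 40 per group are enrolled in Groups 1–3, withdrawn subjects may be replaced, subjects are confined throughout, and a subject with Day 5 but no Day 7 NNAL still contributes to the model. Dunnett's method is normally many-to-one, so four per control is the more natural reading, and on that reading 40 completers alone bring power back to 85–86%. Protocol 11.1 defers detail to the SAP, so an analyst would use Dunnett and the 9% familywise error would not arise. Dunnett is also the stricter rule, so it does not raise the risk of a false primary claim.

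Most of this stands, and it limits the claim: the trial cannot be called underpowered. It does not remove the inconsistency. SAP 4 carries the two-comparison basis inside the SAP itself, so deferring to the SAP does not reconcile the sizing with the test. The SAP never says four per control. SAP 9 tells the reader that everything outside its list is aligned with the protocol, and on this point it is not. Nor does either document offer the retention or covariate argument that would support 85% for the wider family.

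**Conclusion.** The concern holds. The stated 85% belongs to two comparisons at 0.025, not to the Dunnett family in SAP 7.3.1, whose size is undefined and whose use contradicts Protocol 11.9 without being recorded. On the planning basis the shortfall from 85% is about 4 to 6 points for a four-comparison family and about 11 to 13 points for eight jointly. Those sizes rest on the back-solved d of 0.80, exactly 35 completers and no covariate gain. Actual power may reach 85%, but the documents do not show it. Confidence is high in the inconsistency and conditional for the size of the loss. This should be fixed, because the primary p-values and intervals depend on it.

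**What to change.** Define the primary family as Group 2 vs Group 1 and Group 3 vs Group 1 on Day 7 NNAL, tested by Dunnett over those two contrasts or at 0.025 each; either matches the sample size basis. Treat the other group contrasts and Day 5 as secondary, outside that family. Replace the schematic LSMEANS line with explicit within-day contrasts that match Table 14.2.1.1.5.2. Correct the Protocol 11.9 sentence and list the multiplicity change in SAP 9.

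If the wider family is kept, state whether it is four per control or eight jointly and restate power for it: either the planning-basis figure above, or a recalculation for the baseline-adjusted model with effect size, SD and baseline correlation given.

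The cost is SAP wording, a few lines of code and one protocol sentence, with no extra subjects or data. The protocol sentence may need a formal amendment and IRB approval under Protocol 15.3; the SAP 9 entry records the change in either case. The trade-off is that secondary contrasts lose the familywise control they now share with the primary ones, unless they are given a family of their own.

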#### 2.3.2 Secondary Objectives

The secondary objectives are to:

1. To compare biomarkers of exposure (total N-nitrosornicotine [NNN], nicotine equivalents [NE], 2-aminonaphthalene [2-AN], 4-aminobiphenyl [4-ABP], 2-hydroxyethyl mercapturic acid [HEMA], 2-cyanoethyl mercapturic acid [CEMA], S-phenyl mercapturic acid [S-PMA], 3-hydroxy-1-methylpropyl mercapturic acid [3-HMPMA], 3-hydroxypropyl mercapturic acid [3-HPMA], 2-hydroxypropyl-mercapturic acid [2-HPMA], N-acetyl-S-(2-carbamoyl-ethyl)-l-cysteine [AAMA], N-acetyl-S-(2-carbamoyl-2-hydroxyethyl)-l-cysteine [GAMA], 2-hydroxybutenyl-mercapturic acid [2-MHBMA], 2-OH-

Fluorene [2-OHFle], 2-Naphthol, 1-OH-Phenanthrene [1-OHPhe], urine mutagenicity, 1-hydroxypyrene [1-OHP], and carboxyhemoglobin [COHb]) in adult smokers who reduce cigarette consumption by at least 50% with supplementary (dual) usage of VERVE® Chews or VERVE® Discs to those who continue to smoke cigarettes for 5 and 7 days.

2. To compare 24-hour urinary total NNAL in adult smokers who reduce cigarette consumption by at least 50% with supplementary (dual) usage of VERVE® Chews or VERVE® Discs to those who continue to smoke cigarettes for 5 days.
3. To compare biomarkers of exposure (total NNAL, total NNN, NE, 2-AN, 4-ABP, HEMA, CEMA, S-PMA, 3-HMPMA, 3-HPMA, 2-HPMA, AAMA, GAMA, 2-MHBMA, 2-OHFle, 2-Naphthol, 1-OHPhe, urine mutagenicity, 1-OHP and COHb) in adult smokers who reduce cigarette consumption by at least 50% with supplementary (dual) usage of VERVE® Chews or VERVE® Discs to those who cease from all tobacco use for 5 and 7 days.
4. To compare biomarkers of exposure (total NNAL, total NNN, NE, 2-AN, 4-ABP, HEMA, CEMA, S-PMA, 3-HMPMA, 3-HPMA, 2-HPMA, AAMA, GAMA, 2-MHBMA, 2-OHFle, 2-Naphthol, 1-OHPhe, urine mutagenicity, 1-OHP and COHb) in adult smokers who completely switch to VERVE® Chews or VERVE® Discs to those who continue to smoke cigarettes for 5 and 7 days.
5. To compare biomarkers of exposure (total NNAL, total NNN, NE, 2-AN, 4-ABP, HEMA, CEMA, S-PMA, 3-HMPMA, 3-HPMA, 2-HPMA, AAMA, GAMA, 2-MHBMA, 2-OHFle, 2-Naphthol, 1-OHPhe, urine mutagenicity, 1-OHP and COHb) in adult smokers who completely switch to VERVE® usage to those who cease from all tobacco use for 5 and 7 days.

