### **Secondary**

The secondary outcome variables are:

- 24-hour urinary total total NNN, NE, 2-AN, 4-ABP, HEMA, CEMA, S-PMA, 3-HMPMA, 3-HPMA, 2-HPMA, AAMA, GAMA, 2-MHBMA, 2-OHFle, 2-Naphthol, 1-OHPhe, mutagenicity, and 1-OHP excreted on Day 5 and Day 7.
- 24-hour urinary total NNAL excreted on Day 5.
- COHb on Day 5 and Day 7.
- QSU-Brief responses and factor scores on Day 1, Day 5, and Day 7.
- Responses to the appropriate mCEQ on Day 1, Day 5, and Day 7.
- Responses to the appropriate Use the Product Again questionnaire on Day 7.
- Product use behavior daily from Day 1 to Day 7 (i.e., CPD, VPD, and the average and total duration of VERVE® product use each day).

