## **7.3.2 Secondary Endpoint Analysis**

The same statistical analysis model defined in the primary analysis Section 7.3.1 will also be used to make same comparisons as the primary endpoint (i.e. total NNAL on Day 7) for the secondary biomarker endpoints listed in Section 2.4.

These analyses will be conducted on the mITT and PP datasets.

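### The LSMEANS line in SAP 7.3.1 names only Day 7 controls: kept as printed, it over-adjusts the Day 7 comparisons and yields none of the adjusted same-day Day 5 comparisons the table shells require

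*SAP*

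**What the plan says.** SAP 7.3.1 fits one repeated-measures model to the Day 5 and Day 7 values. Its note says: "This model will include both the Day 7 value (primary endpoint) and interim time points (Day 5, secondary endpoint". The prose lists eight pairs, beginning "Pairwise comparisons (Group 2 vs. Group 1, Group 3 vs. Group 1, Group 4 vs. Group 1, Group 5 vs. Group 1" and continuing with the same four test groups against Group 6. These "will be performed using a Dunnett's test at a 2-sided significance level of 0.05 to adjust for multiplicity". No day is attached to the list.

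The section then prints SAS code that it says will be used. The line that requests the comparisons is "LSmeans group*day/CL alpha=0.05 pdiff dunnett ('1'*Day 7, '6'*Day 7".

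SAP 7.3.1.1 adds: "For the test groups compared to the reference groups for each biomarker, Dunnett's method will be used for the adjustment of multiple comparisons". SAP 7.3.2 says the model "will also be used to make same comparisons as the primary endpoint" for the secondary biomarkers.

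Day 5 is a planned time point in its own right. Secondary objective 2 in SAP 2.3.2 compares dual users "to those who continue to smoke cigarettes for 5 days", and the secondary outcomes in SAP 2.4 include "24-hour urinary total NNAL excreted on Day 5".

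In SAP section 12, shell 14.2.1.1.5.2 has a Day 5 row and a Day 7 row for each of the eight comparisons, and its footnote says that Dunnett-Hsu adjusted intervals and p-values are reported. The last-observation-carried-forward shell, 14.2.1.1.7.2, has the same layout and footnote. Where only Day 7 is wanted, as in shell 14.2.1.1.9.3, the title says so.

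**The concern.** The code and the shells ask for different things. The `group*day` effect has a cell for each group on each day, and the line singles out two Day 7 cells as controls. A programmer who turns that directly into a control-cell request sets every other cell, Day 5 cells included, against a Day 7 control.

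Three things follow. The adjustment covers differences that nobody planned, which widens the adjusted Day 7 intervals, including those of the two primary comparisons (Groups 2 and 3 versus Group 1). The Day 5 differences that come out are cross-day, so they mix the group effect with the control group's own change between the two days. And the adjusted same-day Day 5 rows in the shells stay empty. Because SAP 7.3.2 reuses the comparisons, the one omission carries through all 20 biomarkers in the table list.

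The text also leaves the grouping open. It names two control groups under one Dunnett test and does not say whether the family is four per control, eight jointly, or 16 over both days.

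**Working it through.** **Step 1. What the line requests, against what the shell needs.**

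- Cells: 6 groups × 2 days = 12.
- Differences per named control: 12 − 1 = 11. These are 4 test groups on Day 7 (planned), 6 Day 5 cells, and the other control on Day 7.
- Both controls: 2 × 11 = 22 differences. Of these, 2 × 4 = 8 are planned Day 7 rows, 2 × 6 = 12 are cross-day, and 2 are Group 1 versus Group 6 on Day 7.
- Shell 14.2.1.1.5.2: 8 comparisons × 2 days = 16 rows. The line fills 8. The 8 it misses are all the same-day Day 5 comparisons.

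**Step 2. What a cross-day difference estimates.** For Group 2 and Group 1:

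(G2, Day 5 − G1, Day 7) = (G2, Day 5 − G1, Day 5) + (G1, Day 5 − G1, Day 7).

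The last term is the control group's change between days. The documents give no figure for it, so no size is claimed.

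**Step 3. Effect on the adjusted Day 7 intervals.** The SAP states no Dunnett critical value to reproduce. Its sample-size section uses α = 0.025 for each of two comparisons, which gives a critical |t| of 2.261 at 172 degrees of freedom. The 35 completers cannot be reproduced forward, because no effect size or SD is stated.

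Inputs:
- Completers 35/35/35/25/25/25 for Groups 1 to 6 (SAP section 4), 180 in all.
- Degrees of freedom 172 (assumed): 180 − 6 groups − 1 gender − 1 baseline.
- Equal variances across groups and days (assumed).
- Day 5 to Day 7 within-subject correlation ρ of 0.3 to 0.9 (assumed; not in the documents).

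Method: the mean of a cell in group g has variance σ²/n_g, and the two days of one group have covariance ρσ²/n_g. For each family of differences, the critical value is the 95th percentile of the largest |t|, from 1,000,000 simulated draws per ρ.

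| Family | ρ = 0.3 | 0.5 | 0.7 | 0.9 |
|---|---|---|---|---|
| Four same-day, vs Group 1 | 2.47 | 2.47 | 2.47 | 2.47 |
| Printed line, 11 cells vs Group 1 | 2.788 | 2.779 | 2.756 | 2.715 |
| Four same-day, vs Group 6 | 2.455 | 2.455 | 2.455 | 2.455 |
| Printed line, 11 cells vs Group 6 | 2.750 | 2.745 | 2.723 | 2.682 |

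A repeat run at ρ = 0.5, 0.7 and 0.9 agreed with the 11-cell values to within 0.003.

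An adjusted half-width is the critical value × SE. The model, and so the SE, is the same under either family, so the width ratio is the ratio of critical values:

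- Versus Group 1: 2.715/2.47 = 1.10 to 2.788/2.47 = 1.13.
- Versus Group 6: 2.682/2.455 = 1.09 to 2.750/2.455 = 1.12.

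**Step 4. The open grouping.** Eight Day 7 comparisons taken jointly give 2.704, and 2.704/2.47 = 1.09. This does not depend on ρ. Sixteen over both days give 2.85 to 2.93 for ρ between 0.5 and 0.9.

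**The case against.** The strongest reply is that the code is a template. It has unfilled placeholders, and the control list is not valid PROC MIXED syntax, so somebody must rewrite it. SAP 7.3.1 is the primary-endpoint section, where Day 7 controls are natural. The same-day shell rows and SAP 7.3.2 make the Day 5 intention plain. On this view the programmer simply adds the Day 5 controls.

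Much of this stands. The shells do show that same-day contrasts are intended, and cross-day contrasts arise only if the printed logic is kept. But the SAP says this code will be used, and a direct translation keeps exactly that logic: Day 7 control cells within the full `group*day` effect. Invalid syntax does not correct it. Nor does reading `pdiff` as a request for all pairs: that would give same-day Day 5 differences, but unadjusted, not the Dunnett-Hsu results that the footnote requires.

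It is also fair that the family is partly described. Eight pairs and two controls are named, and adjustment stays within a biomarker. Only the grouping by control and by day is missing. On its own that is missing detail.

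A reader might infer inflated type I error, a biased Day 7 estimate, or an underpowered trial. The documents do not support these. A larger family is conservative, the Day 7 differences are unchanged, and no effect size or SD is given from which power could be calculated.

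**Conclusion.** The printed line should not go into production. Kept as it stands, it omits all eight adjusted same-day Day 5 comparisons for each biomarker and makes the adjusted Day 7 intervals about 9 to 13% wider than four same-day comparisons per control would.

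That range rests on the planned completers, equal variances, 172 degrees of freedom and an assumed correlation of 0.3 to 0.9. It also rests on four per control as the benchmark. If the eight pairs were meant as one family (2.704), the 11-cell values versus Group 1 would exceed it by only 0.4 to 3% (2.715/2.704 to 2.788/2.704), although the line would still leave the Day 5 rows empty. The missing Day 5 rows and the unplanned differences follow from the text alone and need no assumption.

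This should be fixed before the analysis is programmed. It does not call the design or the Day 7 estimates into question.

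**What to change.** Replace the line with explicit same-day contrasts on `group*day` (LSMESTIMATE or ESTIMATE): Groups 2 to 5 versus Group 1 and Groups 2 to 5 versus Group 6, at Day 7, and separately at Day 5 against the Day 5 control cells. Apply a simultaneous adjustment, Dunnett-type or simulation-based multivariate-t, over exactly those contrasts within each day. If the simulation-based form is used, reword the Dunnett-Hsu footnotes to match.

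State in one sentence which grouping is used: four per control, or the eight listed pairs jointly. Write the contrasts out one by one. A plain same-day difference-from-control request would bring in the other control group as a fifth comparison and raise the critical |t| to about 2.55 versus Group 1 and 2.52 versus Group 6.

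Use the same code for the secondary biomarkers. Bring the multiple-imputation analysis into line as well: the code in SAP 7.3.4.2 requests plain differences with no Dunnett adjustment, whereas its shell, 14.2.1.1.8.2, reports Dunnett-Hsu results.

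The cost is a few lines of SAS code and one sentence in the SAP. No new data are needed.
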